4.3 Timing of interim analyses

One interim analysis is planned in this study. An interim analysis will be performed when all enrolled patients complete Week 48 (Visit 15) to assess the patient preference after 6 months with deferasirox FCT treatment in comparison to deferasirox DT.

Refer to [Section 2.2](#) and [Section 10](#)

4.4 Definition of end of study

All patients must remain within the study until Week 48 (last visit on Core Phase) unless one of the criteria defined in [Section 7.1.3](#) (definition of premature patient withdrawal) is met, in which case, the patient must discontinue from the study and complete the Study Evaluation Completion Visit (SEC - visit number 777) within 7 days of discontinuing treatment. A patient will be considered as having “completed the study” if all the visits have been performed from Screening (visit number 1) to Week 48 (visit number 15).

The end of study is defined as the earliest occurrence of one of the following:

- The patient has reached Week 96 at Extension phase.
- Deferasirox FCT is locally reimbursed for this indication (only applicable in Extension phase)
- Another clinical study or post-trial access program becomes available that can continue to provide deferasirox FCT in this patient population and all patients ongoing are eligible to be transferred to that clinical study

The investigator will be responsible for informing IRBs and/or EC.

Patients will perform a safety follow up visit 30 days after the last dose of study drug.

4.5 Definition of patient completed

A patient will be considered as having “completed the study” if the patient has completed the core phase of the study, i.e., Week 48.”

4.6 Definition of early study termination

The study can be terminated at any time for any reason by Novartis. Should this be necessary, the patient should be seen as soon as possible and the same assessments should be performed as described in [Section 7](#) for a prematurely withdrawn patient. The investigator may be informed of additional procedures to be followed in order to ensure that adequate consideration is given to the protection of the patient’s interests. The investigator will be responsible for informing IRBs and/or ECs of the early termination of the trial.

5 Population

5.1 Patient population

Approximately 145 patients aged ≥ 2 years, male or female with transfusion-dependent thalassemia or non-transfusion-dependent thalassemia requiring chelation therapy due to iron

overload will be included in this study. Patients may have been previously treated with iron chelators (excluding deferasirox) for at least 6 months or be chelation naïve.

The investigator or designee must ensure that only patients who meet all the following inclusion and none of the exclusion criteria are offered treatment in the study.

5.2 Inclusion criteria

Patients eligible for inclusion in this study have to meet **all** of the following criteria:

1. Prior to any screening procedures being performed, written informed consent/assent must be provided. For pediatric patients, consent will be obtained from the parent(s) or the patient's legal representative. Investigators will also obtain assent of patients according to local, regional or national guidelines.
2. Male and female patients aged ≥ 2 years
3. Deferasirox naïve patient or a chelation naïve patient or a patient treated by other chelators for at least 6 months continuously, such as:
 - a. Deferiprone (DFP)
 - b. Deferoxamine (DFO)
 - c. Combination (DFO + DFP)
4. Subject is willing to discontinue current iron chelation therapy at least 5 days prior to the Study day 1 and for the duration of the study
5. Patients with transfusion-dependent thalassemia (independent of underlying condition) with transfusional iron overload as shown by:
 - a serum ferritin level of > 1000 ng/ml at screening and if available, LIC > 3 mg Fe/g dw within 6 months prior to screening
6. Patients with non-transfusion-dependent thalassemia with iron overload as shown by:
 - a serum ferritin level of ≥ 800 ng/ml at screening and if available, LIC ≥ 5 mg Fe/g dw within 6 months prior to screening

5.3 Exclusion criteria

Patients eligible for this study must not meet **any** of the following criteria:

1. Creatinine clearance below the contraindication limit in the locally approved prescribing information.
2. Serum creatinine level > 1.5 x ULN (upper limit of normal)
3. AST (SGOT) /ALT (SGPT) > 5 x ULN, unless LIC confirmed as >10 mg Fe/dw within 6 months prior to screening visit.
4. Significant proteinuria as indicated by a urinary protein/creatinine ratio > 0.5 mg/mg in a non-first void urine sample.
5. Patients with significant impaired gastrointestinal (GI) function or GI disease that may significantly alter the absorption of oral deferasirox (e.g. ulcerative diseases, uncontrolled nausea, vomiting, diarrhea, malabsorption syndrome, or small bowel resection).
6. Clinical or laboratory evidence of active Hepatitis B or Hepatitis C (HBsAg in the absence of HBsAb OR HCV Ab positive with HCV RNA positive).

7. Patients with psychiatric or addictive disorders which prevent them from giving their informed consent or undergoing any of the treatment options or patients unwilling or unable to comply with the protocol.
8. Patients with a known history of HIV seropositivity (Elisa or Western blot).
9. History of malignancy of any organ system, treated or untreated, within the past 5 years whether or not there is evidence of local recurrence or metastases, with the exception of localized basal cell carcinoma of the skin.
10. Patients participating in another clinical trial or receiving an investigational drug. Patients who have recently completed treatment with an investigational product must have ceased this treatment for at least five times the half-life of the investigational product.
11. History of hypersensitivity to any of the study drug or excipients.
12. Significant medical condition interfering with the ability to partake in this study (e.g. systemic uncontrolled hypertension, unstable cardiac disease not controlled by standard medical therapy, systemic disease (cardiovascular, renal, hepatic, etc.).
13. Women of child-bearing potential, defined as all women physiologically capable of becoming pregnant, **unless** they are using effective methods of contraception during dosing of study treatment. Effective contraception methods include:
 - Total abstinence, when this is in line with the preferred and usual lifestyle of the patient. Periodic abstinence (e.g., calendar, ovulation, symptothermal, post-ovulation methods) and withdrawal are not acceptable methods of contraception.
 - Female sterilization (have had surgical bilateral oophorectomy with or without hysterectomy) or tubal ligation at least six weeks before taking study treatment. In case of oophorectomy alone, only when the reproductive status of the woman has been confirmed by follow up hormone level assessment.
 - Male sterilization (at least 6 months prior to screening). For female patients on the study, the vasectomized male partner should be the sole partner for that patient.
 - Barrier methods of contraception: Condom or Occlusive cap (diaphragm or cervical/vault caps) with spermicidal foam/gel/film/cream/ vaginal suppository.
 - Placement of an intrauterine device (IUD) or intrauterine system (IUS).
 - Please note that deferaxirox may reduce the efficacy of hormonal contraception thus it is recommended to use alternative methods of contraception as described above.
14. Women are considered post-menopausal and not of child bearing potential if they have had 12 months of natural (spontaneous) amenorrhea with an appropriate clinical profile (e.g. age appropriate, history of vasomotor symptoms) or have had surgical bilateral oophorectomy (with or without hysterectomy) or tubal ligation at least six weeks ago. In the case of oophorectomy alone, only when the reproductive status of the woman has been confirmed by follow up hormone level assessment is she considered not of child bearing potential.
15. Sexually active males unless they use a condom during intercourse while taking drug and for 28 days after stopping study medication and should not father a child in this period. A condom is required to be used also by vasectomized men in order to prevent delivery of the drug via seminal fluid.

For prohibited medication please refer to [Section 6.3.2](#).

Eligibility criteria must be reviewed prior any study treatment is given.

6 Treatment

6.1 Study treatment

The sponsor will provide the following open label study medication:

- Deferasirox DT will be provided as 125 mg, 250 mg and 500 mg dispersible tablets for oral use.
- The strengths provided in an individual country may differ and will reflect the strengths available commercially in each country
- Deferasirox FCT will be provided as 90 mg, 180 mg and 360 mg film-coated tablets for oral use.

Once a patient meets one of the end of study criterion (see [Section 4.4](#)), he/she will be discontinued from the study, a SEC visit will be completed and will be followed up for safety purposes 30 days after the last dose of study drug. If the patient is to continue on Deferasirox FCT after discontinuing from the study, this will be using commercially available deferasirox FCT (Jadenu®) as 90 mg, 180 mg and 360 mg film-coated tablets for oral use.

For this study, the terms “investigational drug”, “study drug” and “study treatment” refer to deferasirox FCT as well as deferasirox DT.

6.1.1 Dosing regimen

Having completed the screening period (including the 5-day wash-out period for patients previously treated with Deferiprone/DFP or Deferoxamine/DFO), eligible patients will start the core phase and be switched on the Day 1 visit to deferasirox DT for 24 weeks followed by deferasirox FCT for 24 weeks duration. Upon completion of Week 48 (Core Phase), the patient can still be treated with deferasirox FCT for a maximum of another 48 weeks or until one of the end of study criteria defined is met, whichever comes first.

The starting dose on Baseline Day 1 would be as following:

- Deferasirox DT of 20 mg/kg/day in transfusion-dependent thalassemia (TDT)
- Deferasirox DT of 10 mg/kg/day in non- transfusion-dependent thalassemia (NTDT),

Table 6-1 Equivalent FCT starting dose at Week 25

Equivalent dose to be used	
Deferasirox DT (mg/kg/day)	Deferasirox FCT (mg/kg/day)
5	3.5
10	7
15	10.5
20	14
25	17.5
30	21

Equivalent dose to be used	
Deferasirox DT (mg/kg/day)	Deferasirox FCT (mg/kg/day)
35	24.5
40	28

All iron chelation pre-treated patients who had received treatment with deferoxamine (DFO) and deferiprone (DFP) will be initiated on deferasirox DT. The dose of deferiprone will be determined by their serum ferritin and the dose of deferoxamine by using the equivalent deferasirox DT dose (see [Appendix 14.2](#)).

Dose adjustment for better treatment effects, based on serum ferritin levels and investigator's judgment, will be allowed for ICT naïve patients after 4 weeks of study treatment and for ICT pre-treated patients every 3 months. The dose adjustments will be performed in steps of 5-10 mg/kg/day for deferasirox DT or in steps of 3.5-7 mg/kg/day for deferasirox FCT.

For each patient the daily dose is calculated by the physician based on the patient's actual body weight, and then rounded up or down to the nearest whole tablet according to the available strengths of deferasirox tablets (125 mg, 250 mg and 500 mg for the DT and 90 mg, 180 mg and 360 mg for the FCT, see [Appendix 14.1](#)).

The investigator should instruct the patient (or legal patient's representative in the case of pediatric patients) to take the study drug as prescribed. All doses planned and prescribed to the patient and all dose changes including reasons for change during the study must be recorded in the eCRF.

During the regular study visits, the investigator or pharmacist will dispense to the patient or the patient's legal representative, an appropriate number of deferasirox tablets depending on the patients calculated dose. The number of tablets of each strength dispensed will be recorded in the Subject IMP dispensing and accountability log. Each time the deferasirox study drug is dispensed to the patient and/or legal patient's representative, the investigator will provide detailed instructions on how to prepare and administer the dose. Patients or the patient's legal representative will be instructed to take/administer the assigned amount of study drug and will be obliged to return all unused study medication every 4 weeks. Study medication returned by the patient or the patient's legal representative will be counted and unused study medication will be recorded by the investigator or pharmacist involved in the study. Drug accountability will be verified by the field monitor during site visits and at the completion of the trial.

Medication labels will comply with the legal requirements of the countries where the study is implemented and be printed in the local language. They will supply no information about the patient. Only the patient identifier will be entered on the medication label by the investigator or pharmacist before the corresponding medication is handed out to the patient. The storage conditions for study drug will be described on the medication label.

Patients on deferasirox DT period will take the deferasirox DT every day (not later than 12:00 PM) on an empty stomach, at least 30 minutes before the next meal. The patient will disperse the required number of deferasirox DT in a glass of water, apple juice or orange juice. Gentle stirring should be applied and continued until the tablets are fully disintegrated, which takes approximately 1 to 3 minutes. Immediately, after full disintegration of the tablets, the entire content of the glass should be swallowed.

Patients on deferasirox FCT will swallow the required number of deferasirox FCT every day (not later than 12:00 PM) with or without a light meal. For patients with difficulties in swallowing Deferasirox FCT, it is allowed to crush the film-coated tablets. They should be administered by sprinkling the full dose on soft food like yogurt or apple sauce (apple puree).

All patients should take their deferasirox dose (DT or FCT) before 12:00 PM (noon).

Dose adjustments based on safety are allowed at any time point in the study and will be in increments of 5-10 mg/kg/day for deferasirox DT or 3.5-7 mg/kg/day for deferasirox FCT. Dose adjustments based on efficacy are permitted. For ICT naïve patients at study entry dose adjustments are allowed after 4 weeks of study treatment based on serum ferritin levels and investigator's judgement. For ICT pre-treated patients, the dose of deferasirox should be adjusted if necessary every 3 months based on the trends in serum ferritin and investigator's judgement. For more details please refer to [Table 6.2](#) – Dose of study drug based on serum ferritin level.

Table 6-2 Dose and treatment schedule

Study treatments	Pharmaceutical form and route of administration	Starting Dose* (weeks 1-4)	Dose adjustment (after week 4)	Max dose	Frequency and/or Regimen
Deferasirox DT – TDT patients	Dispersible tablets, p.o.	20 mg/kg/day	+ 5 - 10 mg/kg/day	40 mg/kg/day	Once daily
Deferasirox DT – NTD patients	Dispersible tablets, p.o.	10 mg/kg/day	+ 5 - 10 mg/kg/day	20 mg/kg/day	Once daily
Deferasirox FCT – TDT patients	Film-coated tablets, p.o.	14mg/kg/day	+ 3.5 - 7 mg/kg/day	28 mg/kg/day	Once daily
Deferasirox FCT – NTD patients	Film-coated tablets, p.o.	7 mg/kg/day	+ 3.5 - 7 mg/kg/day	14 mg/kg/day	Once daily

*Iron chelation naïve patients. All iron chelation pre-treated patients see [Section 6.1.1](#) and [Appendix 14.2](#) for guidance.

Table 6-3 Daily dose of study drug based on serum ferritin level

Dose Regimen of Drug for TDT patients	Serum ferritin level
20 mg/Kg Deferasirox DT 14 mg/Kg Deferasirox FCT	1000-1500 ng/ml
30 mg/Kg Deferasirox DT 21 mg/Kg Deferasirox FCT	>1500-2000 ng/ml
40 mg/Kg Deferasirox DT 28 mg/Kg Deferasirox FCT	>2000 ng/ml
Dose Regimen of Drug for NTD patients	Serum ferritin level
5 mg/Kg Deferasirox DT 3.5 mg/Kg Deferasirox FCT	300-799 ng/ml
10 mg/Kg Deferasirox DT	800-2000 ng/ml

Dose Regimen of Drug for TDT patients	Serum ferritin level
7 mg/Kg Deferasirox FCT	
20 mg/Kg Deferasirox DT 14 mg/Kg Deferasirox FCT	>2000 – 4000 ng/ml
30mg/Kg Deferasirox DT 21mg/Kg Deferasirox FCT	>4000ng/mL

Serum ferritin level will be measured monthly to evaluate the study drug response

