6.2.1.4 Changes in urine protein/creatinine ratio

Proteinuria should be monitored during the study as stated in [Table 7-1](#) and [Table 7-2](#).

In case of a single increase of the urinary protein/creatinine ratio the assessment should be repeated at the next visit.

Deferasirox dose reduction by 50% should be performed if the urinary protein/creatinine ratio increases to > 0.5 mg/mg in two consecutive second-void urine samples (a minimum of 48h apart), if all other causes of proteinuria have been excluded.

Deferasirox must be temporarily interrupted if the urinary protein/creatinine ratio increases to > 1.0 mg/mg in two consecutive second-void urine samples (a minimum of 48h apart).

Should proteinuria persist, study treatment may be discontinued if the investigator believes it is in the best interest of the patient. Novartis may be contacted by the investigator to discuss dosing options if the investigator so desires.

Dose adjustment will be based on local laboratory results.

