| S03                 | Deferasirox DT and/or FCT is not compliant with Protocol table 6-3 based on serum ferritin levels.  | EXCLUDE FROM PPS             | 4                    |
| S04                 | Study dose should be adjusted if there is a change in body weight (increase or decrease) of minimum 10% compare to visit 2 or last dose adjustment due to change in patient's body weight.                    | EXCLUDE FROM PPS             | 4                    |
| S05                 | Patient in period 1 of Core phase received Deferasirox FCT by error (except patients who switched from Deferasirox DT to Deferasirox FCT)   | EXCLUDE FROM FAS             | 1                    |
| S06                 | Patient in period 2 of Core phase or extension phase took Deferasirox DT by error (except patients who switched from Deferasirox FCT to Deferasirox DT).  | EXCLUDE FROM FAS             | 1                    |
| S07a                | Patient re-switched treatment within the same period of the study (that is, patient switched from Deferasirox DT to Deferasirox FCT and the switch back to Deferasirox DT)                                    | EXCLUDE FROM FAS             | 1                    |
| S07b                | Patient re-switched treatment within the same period of the study (that is, patient switched from Deferasirox FCT to Deferasirox DT, and then back to Deferasirox FCT)  | EXCLUDE FROM FAS             | 1                    |

| Deviation ID | Description of Deviation   | Exclusion in Analyses | Severity code |
|--------------|--|-----------------------|---------------|
| S08          | Iron chelation pre-treated patient who is well-managed on treatment with deferoxamine DFO/deferiprone DFP or combination of DFO+DFP did not receive the equivalent deferasirox DT/FCT dose per app. 14.1 | EXCLUDE FROM PPS      | 4             |
| S09          | Dose adjustment (based on Serum ferritin levels and investigator's judgement) in ICT naïve patients done before 4 weeks of study treatment and it was not performed for safety reasons                   | EXCLUDE FROM PPS      | 4             |
| S10          | Dose adjustment (based on Serum ferritin levels and investigator's judgement ) ICT pre-treated patients done before 3 months of study treatment and it was not performed for safety reasons              | EXCLUDE FROM PPS      | 4             |

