| S11          | The dose adjustment in deferasirox DT not performed in increments of 5-10 mg/kg/day  | INCLUDE IN EVERYTHING | 0             |
| S12          | The dose adjustment in deferasirox FCT not performed in increments of 3.5-7 mg/kg/day  | INCLUDE IN EVERYTHING | 0             |
| S13          | Deferasirox dose was not temporarily interrupted despite urinary protein/creatinine ratio increases to > 1.0 (mg/mg) in two consecutive second-void urine samples (a minimum of 48h apart)               | INCLUDE IN EVERYTHING | 0             |
| S14          | Deferasirox dose was not temporarily interrupted even though the skin rash persists for > 1 week or becomes more severe  | INCLUDE IN EVERYTHING | 0             |
| S15          | Maximum dose of deferasirox DT is not compliant with Protocol table 6-2.   | EXCLUDE FROM PPS      | 4             |
| S16          | Maximum dose of deferasirox FCT is not compliant with Protocol table 6-2.  | EXCLUDE FROM PPS      | 4             |
| S17          | Dose adjustment of deferasirox DT is not compliant with Protocol table 6-2.  | EXCLUDE FROM PPS      | 4             |
| S18          | Dose adjustment of deferasirox FCT is not compliant with Protocol table 6-2.   | EXCLUDE FROM PPS      | 4             |
| S19          | Patient received incorrect dose due to dispensing error.   | Include in Everything | 0             |
| S20          | Cautious re-initiation of Deferasirox treatment at a lower dose was not done following Study medication interruption due to Increased liver enzyme levels (ALT/AST).                                     | Include in Everything | 0             |

| Deviation ID | Description of Deviation  | Exclusion in Analyses | Severity code |
|--------------|---|-----------------------|---------------|
| S21          | Deferasirox dose reduction by 10 mg/kg/day for the DT formulation and by 7 mg/kg/day for the FCT formulation was not performed following a rise in serum creatinine by 33% above baseline value resulting in a serum creatinine above the ULN on two consecutive visits (a minimum of 7 days apart) | Include in Everything | 0             |
| S22          | Resuming study medication dose is not done according to protocol following treatment interruption for abnormal Serum Creatinine.  | Include in Everything | 0             |

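### The event-specific safety dose rules in Protocol 6.2.1 fall outside the general step in 6.1.1 and 2.3, and SAP 5.5 codes S03, S11, S12, S17 and S18 have no safety exemption, so correct dosing can be logged as a deviation or cost a patient the PPS

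*Protocol*

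**What the plan says.** **General rule.** Protocol 6.1.1: "Dose adjustments based on safety are allowed at any time point in the study and will be in increments of 5-10 mg/kg/day for deferasirox DT", with 3.5-7 mg/kg/day for FCT. Section 2.3 gives the permitted adjustment as plus or minus the same amounts. Neither mentions an exception or points to Section 6.2.1.

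**Event-specific rules.**
- Section 6.2.1.4: "Deferasirox dose reduction by 50% should be performed if the urinary protein/creatinine ratio increases to > 0.5 mg/mg" in two consecutive second-void samples at least 48 hours apart, and only "if all other causes of proteinuria have been excluded".
- Section 6.2.1.2: after a creatinine interruption, restart at 50% of the last dose is recommended, with return to 100% allowed after one month.
- Section 6.2.1.5: after interruption for a rash that persists beyond a week or worsens, resume at 50% and go back to 100% after two weeks if it does not recur.
- The Section 6.2.1 lead-in asks for a written request to the sponsor only for adjustments that its subsections do not cover.

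**SAP 5.5, Table 1.**
- S11 and S12 (code 0, kept in every analysis): "The dose adjustment in deferasirox DT not performed in increments of 5-10 mg/kg/day" and "The dose adjustment in deferasirox FCT not performed in increments of 3.5-7 mg/kg/day".
- S17 (code 4, out of the PPS): "Dose adjustment of deferasirox DT is not compliant with Protocol table 6-2"; S18 is the FCT equivalent.
- S03 (code 4) flags a dose that does not match the ferritin bands of Protocol Table 6-3.
- None of these five exempts safety changes. S09 does, for an adjustment "done before 4 weeks of study treatment and it was not performed for safety reasons", and S10 carries the same exemption for pre-treated patients.

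**The concern.** A site that follows the proteinuria, creatinine-restart or rash rule at a higher dose makes a change larger than the only step size that Sections 6.1.1 and 2.3 allow. Two things are then at stake.

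The first is clarity of a safety instruction in a trial that enrols from age 2. A site that applied the general step to confirmed proteinuria would cut by less than half.

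The second is classification. The SAP codes test the general step, Table 6-2 and Table 6-3, without asking whether the change was made for safety. Correct management can therefore appear in the deviation listing, and under the code 4 rows it can remove the patient from the PPS, which the SAP uses as a supportive check on the primary analysis.

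**Working it through.** **Inputs.** Dose levels: Protocol Table 6-1 (DT 5 to 40; FCT = 0.7 x DT). Step: 5-10 DT, 3.5-7 FCT (Sections 6.1.1 and 2.3). Safety rules: Sections 6.2.1.2, 6.2.1.4 and 6.2.1.5. Codes: SAP 5.5. The plan gives no figure of its own to reproduce.

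**Step 1: halving against the step.** At DT level d the cut is d/2. One largest step leaves d - 10, and the ratio to the halved dose is (d - 10)/(d/2).

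| DT | Cut d/2 | Within 5-10? | One step leaves | Halved dose | Ratio |
|---|---|---|---|---|---|
| 5 | 2.5 | no, below | - | 2.5 | - |
| 10 | 5 | yes | - | 5 | - |
| 15 | 7.5 | yes | - | 7.5 | - |
| 20 | 10 | yes | 10 | 10 | 1.00 |
| 25 | 12.5 | no, above | 15 | 12.5 | 1.20 |
| 30 | 15 | no, above | 20 | 15 | 1.33 |
| 35 | 17.5 | no, above | 25 | 17.5 | 1.43 |
| 40 | 20 | no, above | 30 | 20 | 1.50 |

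FCT behaves alike. Cuts of 8.75, 10.5, 12.25 and 14 at 17.5, 21, 24.5 and 28 exceed 7; 1.75 at 3.5 is below 3.5; 3.5, 5.25 and 7 at 7, 10.5 and 14 fit.

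**Step 2: tablets at 50 kg.** DT 40 is 2000 mg (Table 14-8), one step down 1500 mg (Table 14-6), halved 1000 mg (Table 14-4). FCT 28 is 1440 mg (Table 14-16), one step down 1080 mg (Table 14-14), halved 720 mg (Table 14-12). Rounding blurs the edges. For DT 25 at about 12.5-13.9 kg the tablet dose is 250 mg, and its half is 125/12.5 = 10.0 down to 125/13.9 = 9.0 mg/kg, which is within the step.

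**Step 3: restart and return.** Restart at half of last dose d, then return to d, is a fall and a rise of d/2, so the table applies again. Rash at DT 40: 40 to 20, then 20 to 40, a rise of 20. Under Section 6.2.1.2 the interruption follows an earlier cut of 10, so a patient who began at DT 40 has last dose 30, restarts at 15 and returns with a rise of 15. The creatinine reduction itself (10 DT, 7 FCT) fits the step.

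**Step 4: the codes.**
- *S11/S12.* All the changes above that lie outside the step meet these definitions. For the creatinine restart at last dose 30, S22 flags a site that does not follow the protocol, and S11 flags one that does.
- *S17/S18.* Table 6-2 prints the adjustment with a plus sign. Read as increases only, it does not reach the proteinuria cut, but a return from DT 20 to 40 (+20) still exceeds +10. Read as covering both directions, it reaches the cut as well.
- *S03.* Table 6-3 assigns DT 40 to a TDT patient with ferritin above 2000 ng/ml. While ferritin stays there, a halved dose of 20 or a creatinine-reduced dose of 30 both fail to match. S03 therefore also reaches safety reductions that respect the general step.

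**Step 5: which analyses move.** SAP 5.5 Table 2 excludes from the FAS only on codes 1 and 3. The five rows carry 0 or 4, so the FAS is unchanged.

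**The case against.** The best defence is that Section 6.2.1 is itself the departure from Section 6.1.1. Its lead-in requires sponsor authorisation only for adjustments that its subsections do not cover, and proteinuria is covered. Percentage rules recur there (restart at 50% after creatinine interruption or rash), so the event-specific rules are evidently not tied to the 5-10 range. This largely stands. A reader might infer that patients will be left on 20% to 50% more drug than intended. The documents do not support that: it needs a site to put the general sentence above the proteinuria section and also to stop at one step. Interruption above 1.0 mg/mg applies regardless.

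A second argument is that increments set only the grain of a change, so two may be combined. Section 2.3 weakens this, because there the permitted adjustment itself is plus or minus 5-10 DT (3.5-7 FCT). Combining steps also cannot produce the 2.5 cut at DT 5 or the 1.75 cut at FCT 3.5.

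A third is that the Table 6-2 column, headed as applying after week 4 and printed with a plus sign, describes ferritin titration. That is a fair reading, and it makes PPS exclusion for the halving itself uncertain under S17/S18. It does not deal with the return to full dose or with S03.

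Finally, S11/S12 are code 0 and exclude no one. That is correct, but the listing would still label compliant care as a deviation.

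**Conclusion.** The point holds in two parts of unequal strength.

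1. **Protocol text: an ambiguity.** The stated step and the Section 6.2.1 rules disagree at DT 25-40 and FCT 17.5-28 (1.25 to 2 times the largest step) and at DT 5 and FCT 3.5 (half the smallest step). The upper range concerns mainly TDT patients. This takes the NTDT cap of DT 20 in Sections 2.3 and 6.2.1.3 as binding, although Table 6-3 lists DT 30 for NTDT ferritin above 4000 ng/ml. Table 6-3 assigns DT 30 or 40 to TDT patients above 1500 ng/ml, so the levels are ordinary ones in the plan.

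2. **SAP 5.5: wrong as written.** S11/S12 record compliant safety dosing as a deviation. S17/S18 and S03 can remove such a patient from the PPS. This rests on applying the codes literally; a sensible data review might override them, but no rule tells it to.

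Three stronger conclusions may tempt a reader and are not supported. The primary result is not at risk, because the FAS does not use these codes. Exclusion from the PPS for halving is not certain. The lack of a code for a missed 50% cut, when S13 covers "Deferasirox dose was not temporarily interrupted despite urinary protein/creatinine ratio increases to > 1.0", is a choice about what to list and not an error. The documents do not say how many patients would be affected.

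**What to change.** - **Protocol 6.1.1 and 2.3:** add after the step size: 'except where Section 6.2.1 specifies a different reduction, restart or re-escalation dose, which then governs'.
- **SAP 5.5:** limit S03, S11, S12, S17 and S18 to adjustments not made under the safety rules of Section 6.2.1, in the manner of S09/S10. S03 must be included; otherwise a patient halved from DT 40 with ferritin still above 2000 ng/ml can leave the PPS even after the other four rows are corrected.
- **Optional:** a code 0 row for a 50% cut not made when all conditions of Section 6.2.1.4 were met.

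Cost: one clause in two protocol sections and edits to five SAP rows. Visits, sample size and the primary analysis stay as they are. The reason for each dose change is already recorded in the eCRF (Section 6.1.1), so no new data are needed. The SAP document history places the current version after the interim database lock, so any change to the code 4 rows should be dated and declared as such.
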